3.1 Screening Data, Eligibility, and Recruitment

Participants are identified and screened according to the procedures described in the study protocol (Protocol Section 5). Screening data will be summarized to describe the representativeness of the study population and to document participant flow through the trial.

The total number of participants assessed for eligibility at screening will be summarized, together with the number and reasons for screen failures. Reasons for ineligibility will be categorized according to violations of inclusion and exclusion criteria as defined in the protocol.

Screening and eligibility data will be presented using descriptive summaries

3.2 Baseline Participant Characteristics

Baseline demographic and clinical characteristics will be summarized by randomized treatment arm and overall, for all randomized participants. Baseline characteristics will also be summarized for the primary analysis population to assess the potential impact of attrition on group balance.

The following baseline variables will be summarized, as available:

- Age (years)
- Sex
- Education level (if collected)
- Body weight, height, and body mass index (BMI)
- Alzheimer's disease stage (early vs mild AD)
- Baseline cognitive measures (MMSE, MoCA)
- Baseline exosome biomarker levels
- Baseline use of concomitant medications relevant to cognition or safety

Baseline characteristics will be summarized using descriptive statistics:

- Continuous variables: number of observations, mean, standard deviation, median, interquartile range (25th–75th percentile), minimum, and maximum
- Categorical variables: number and percentage of participants

No formal statistical comparisons between treatment groups will be performed. Any clinically relevant imbalances between treatment arms will be described qualitatively.

3.3 Withdrawal and Follow-up

Participant disposition and withdrawal status will be summarized by treatment group. Levels of withdrawal will be categorized as follows:

- Completed study intervention and all scheduled assessments
- Completed scheduled assessments but did not complete study intervention
- Withdrew from study intervention but continued follow-up
- Withdrew consent for further participation
- Lost to follow-up

The number and percentage of participants in each category will be tabulated by treatment arm and overall. Reasons for withdrawal or loss to follow-up will be summarized descriptively.

Participants who discontinue study treatment but provide post-baseline outcome data will be included in the relevant analysis populations according to the definitions specified in Section 4. Early termination visits will be mapped to the end-of-treatment time point where applicable.

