6.8.5. Rescue Medicine

The study site will not supply rescue medication.

7. Monitoring of Study Intervention and Participant Discontinuation/Withdrawal

Participants may choose to withdraw from the study at any time and for any reason. Participants may be withdrawn from the study if it is in their best clinical interest by the site Investigator.

Participants who drop out of the study will be recorded as either defaulters or withdrawn.

‘Defaulters’ are participants who withdraw their consent to participate in the trial, affecting both treatment and assessment. No further assessments can be made of these participants.

‘Withdrawn’ are participants who are withdrawn from treatment at the discretion of the chief investigator because of clinical factors, poor compliance, or a change in circumstances.

Withdrawn participants will remain in the study and trial assessments will still be undertaken.

The reason for dropping out will also be recorded.

Every effort will be made to collect outcome data on all participants who withdraw from treatment for whatever reason. If participants withdraw from treatment, all endpoint assessments will be carried out at the point of drop-out and at the 8-week endpoint unless consent is withdrawn.

This study is unblinded with respect to the treatment assignment so both the participant and site staff will know which treatment modality the participant received.

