7.2. Procedures for Participant Discontinuation

In rare instances, it may be necessary for a participant to permanently discontinue the study intervention. If the study intervention is permanently discontinued, the participant should, if at all possible, remain in the study to be evaluated for safety, tolerability, and efficacy outcomes. See the Schedule of Assessments (SoA) for data to be collected at the time of discontinuation of study intervention and follow-up, and for any further evaluations that need to be completed. Participants who discontinue the study intervention should undergo the following procedures:

1. **Documentation of Reason for Discontinuation:** The reason for discontinuation must be documented in detail, including any adverse events, lack of efficacy, non-compliance, or personal reasons.
2. **Outcome data:** Every effort will be made to collect outcome data on all participants who withdraw from treatment for whatever reason. If participants withdraw from treatment, all endpoint assessments will be carried out at the point of drop-out and at the 12-month endpoint unless consent is withdrawn.

As PATH-1 is unblinded there will be no procedures related unblinding of the participants

8. Required Actions and Follow-Up

1. Reporting:

- All events of ALT or AST $\geq 3 \times$ ULN and total bilirubin $\geq 2 \times$ ULN (with $> 35\%$ direct bilirubin) or ALT or AST $\geq 3 \times$ ULN and INR > 1.5 or GFR < 30 mL/min/1.73 m²) and acute kidney injury (e.g., serum creatinine increase by 1.5 times baseline or oliguria) must be reported to the sponsor in an expedited manner.
- Additionally, QTc prolongation ≥ 460 milliseconds for males or ≥ 470 milliseconds for females, significant arrhythmias (e.g., Torsade de Pointes), or bradycardia with heart rate < 50 bpm and associated symptoms (e.g., syncope) must also be reported within 24 hours. Confirmed gastrointestinal bleeding, such as melena, hematemesis, or peptic ulcers, persistent severe symptoms not resolving with management (e.g., uncontrolled vomiting), should be reported as serious adverse events (SAEs) when applicable. All adverse events must be documented in the case report form (CRF) and reported to the study sponsor regulatory authorities according to local requirements.

2. Follow-Up

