10.3. Statistical Analyses

All primary, secondary and exploratory outcomes will be collected for all participants, except that PK analyses will be performed only for participants randomized to phenserine.

Trial management and data management will be conducted by the University Hospital Stavanger Clinical Trials Unit and the trial statistics will be led by [name], King's College London.

Standard safety data (including all AEs, TEAEs, SAEs, important clinical laboratory findings, and AE-related discontinuations) will be summarized for each treatment arm and dose level.

Exosome biomarker values will be natural log transformed to avoid skewness. To assess the effect of phenserine on a given biomarker, a linear mixed-effects model will be used, with treatment groups (phenserine vs donepezil), time, baseline biomarker, and plate to plate variability in exosome concentration (determined by NanoSight) as fixed effects and participant identification treated as a random effect.

To demonstrate that dropout rates are Missing at Random (MAR), we will calculate the correlation between dropout indicators (e.g., whether a participant drops out) and key covariates, including treatment group, baseline characteristics, and other relevant random effect categories. Based on prior observations (liraglutide trial for example), we expect that the likelihood of dropout will largely be explained by observed factors, especially drug treatment status. A logistic regression model will be used, with the dropout indicator as the dependent variable and treatment status, baseline covariates, and any other relevant factors as independent variables. If the model explains a significant portion of the dropout pattern, this would support the MAR assumption. Sensitivity analyses will also be conducted to assess the robustness of this finding under alternative missingness mechanisms.

For clinical secondary and exploratory outcomes, change from baseline will be calculated at the final study assessment (mean, n, standard deviation, standard error, minimum and maximum scores).

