2.4 Timing of Outcome Assessments

The timing of all outcome assessments is predefined in the study protocol and summarized in the Schedule of Activities (SoA) (Protocol Section 1.3, Table 1). Outcome measures are collected at screening, baseline, and at scheduled on-treatment and follow-up visits during the 8-week treatment period and safety follow-up.

For all clinically planned outcome measures, visits should occur within the predefined visit windows. Assessments performed outside the allowable visit window will be considered protocol deviations, unless otherwise justified and documented. Only assessments obtained within the protocol-specified windows will be used for primary and secondary analyses.

The target days and visit windows relevant for efficacy, pharmacodynamic, pharmacokinetic, and safety analyses are defined as follows:

Visit Label	Visit Window
Screening	Within 28 days prior to baseline
V1: Baseline / Randomization	Day 0
V2: Week 2	Day 14 ± 3 days
V3: Week 4	Day 28 ± 3 days
V4: Week 6	Day 42 ± 3 days
V5: Week 8 / End of Treatment	Day 56 ± 3 days
Safety Follow-up / EOS	Within 28 days after last dose

Assessments collected outside the visit window will not be included in the primary analysis but may be listed and summarized descriptively.

3 Study Design Overview

- Design: Open-label, randomized (6:2), parallel-group Phase 1b study
- Treatment Arms:
 - Phenserine (dose-escalation up to 10 mg TDS)
 - Donepezil (5–10 mg OD)
- Treatment Duration: 8 weeks
- Sample Size: n = 16 (Phen: n=12; Donepezil: n=4)

Given the exploratory nature and small sample size, all analyses will be descriptive, and estimation focused.

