3.4.2 Protocol Deviations

A protocol deviation is defined as any departure from the approved protocol, including but not limited to deviations related to eligibility criteria, study treatment administration, study assessments, or visit scheduling.

Protocol deviations will be prospectively classified as major or minor prior to database lock and prior to unblinding of biomarker results.

Major Protocol Deviations

Major protocol deviations are defined as deviations that may affect participant safety, the scientific integrity of the study, or the interpretability of the primary endpoint.

Predefined major protocol deviations include:

- Failure to meet inclusion or exclusion criteria with enrolment into the study
- Receipt of incorrect study treatment or dose not consistent with protocol-defined escalation rules
- Discontinuation of study treatment prior to completion of the dose-escalation phase without post-baseline biomarker data
- Use of prohibited concomitant medication with potential impact on safety or pharmacodynamic outcomes
- Missing all post-baseline exosome biomarker assessments

Participants with major protocol deviations may be excluded from specific analysis populations as defined in Section 4.

Minor Protocol Deviations

Minor protocol deviations include deviations that are not expected to materially affect safety or interpretation of study outcomes, such as:

- Study visits conducted outside the protocol-defined visit window
- Isolated missed or delayed assessments
- Administrative or documentation errors

Summary of Protocol Deviations

Protocol deviations will be summarized descriptively by treatment group and overall. The following summaries will be provided:

- Number and percentage of participants with at least one protocol deviation
- Number and percentage of participants with at least one major protocol deviation
- Number and percentage of participants with at least one minor protocol deviation

- Listing of protocol deviations by category and type

Percentages will be calculated using the randomized population as the denominator. No formal statistical testing will be undertaken.

4 Analysis Populations

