4.5 Overview of Outcomes

An overview of the primary, secondary, and exploratory outcomes included in the PATH-1 study is provided in Table 4.4-1. Outcomes are categorized by level, timeframe, and data type to clarify their role in the statistical analyses.

Overview of Study Outcomes

Level	Outcome	Timeframe	Outcome Type
Primary	Change from baseline in exosome biomarkers of pre-programmed cell death, synaptic integrity, neuroinflammation, and AD-related protein trafficking	Baseline to Week 8	Continuous
Secondary (Key)	Safety and tolerability (AEs, SAEs, labs, ECGs, vital signs)	Throughout study	Categorical / Continuous
Secondary	Steady-state pharmacokinetic parameters (e.g. plasma concentrations)	Weeks 2–8	Continuous
	Proportion achieving target AChE inhibition (~45%)	During treatment	Dichotomous
	Time to achievement of target AChE inhibition	During treatment	Time-to-event
	Duration of maintenance of target AChE inhibition	During treatment	Continuous

	Treatment compliance (capsule count, diary)	During treatment	Continuous / Categorical
Exploratory	Change in CSF biomarkers (A β 1-40, A β 1-42, Tau, p-tau)	Baseline to Week 8	Continuous
	Change in plasma biomarkers (p-tau217, NfL)	Baseline to Week 8	Continuous
	Change in FLAME cognitive domain scores	Baseline to Week 8	Continuous
	Change in MoCA total score	Baseline to Week 8	Continuous

5 General Statistical Principles

- All analyses will be conducted using R (version ≥ 4.2) or SAS (version ≥ 9.4)
- Continuous variables: mean, SD, median, IQR, min, max
- Categorical variables: counts and percentages
- No formal hypothesis testing or multiplicity correction
- Emphasis on effect size estimation, confidence intervals, and visualizations
- Outliers and extreme values in biomarker measurements will be retained in primary analyses unless determined to result from assay or data collection errors. Sensitivity analyses may exclude extreme values (e.g., >10 MAD from median) to assess their influence on results. If performed, such analyses will be justified and documented.
- No formal subgroup analyses are pre-planned. Exploratory descriptive summaries may examine biomarker responses by baseline disease severity (early vs. mild AD) or by achievement of target AChE inhibition, but these will be clearly labeled as descriptive and post-hoc.

6 Handling of Missing Data

- No imputation will be performed for missing biomarker or cognitive data
- Analyses will use observed data only in a complete-case manner

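### The SAP's rules for early-termination and out-of-window samples conflict, so the Week 8 exosome dataset is not uniquely defined and its contrast can be biased or lose precision

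*SAP*

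**What the plan says.** Five places govern which samples reach the Week 8 comparison.

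- SAP 3.3, on participants who stop: "Early termination visits will be mapped to the end-of-treatment time point where applicable". The qualifier at the end is not defined.
- SAP 2.4: "Only assessments obtained within the protocol-specified windows will be used for primary and secondary analyses". Its window table sets Week 8 at Day 56 ± 3 and is said to apply to safety as well as biomarker analyses. Its closing sentence allows out-of-window data to be listed and summarised.
- SAP 3.4.2 lists among the minor deviations, which it does not expect to matter for safety or interpretation: "Study visits conducted outside the protocol-defined visit window".
- SAP 6: "No imputation will be performed for missing biomarker or cognitive data" and "Analyses will use observed data only in a complete-case manner". It also keeps early terminators in wherever they have data.
- Protocol section 7, for those who stop treatment: "all endpoint assessments will be carried out at the point of drop-out and at the 8-week endpoint unless consent is withdrawn". Protocol 7.2 has the same rule with a different time point: "all endpoint assessments will be carried out at the point of drop-out and at the 12-month endpoint unless consent is withdrawn".

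The primary population (SAP 4.3) needs one dose and one post-baseline exosome sample. SAP 7.2 plans mean change differences with 95% intervals and a random-intercept model over Weeks 2, 4, 6 and 8, falling back to description if the model does not converge. Protocol 10.3 proposes a logistic regression of drop-out and says of it: "If the model explains a significant portion of the dropout pattern, this would support the MAR assumption". It then promises sensitivity analyses under other missingness mechanisms. SAP 6 contains none.

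**The concern.** Using an early sample as the Week 8 value amounts to carrying a value forward, in a plan that says it does not impute. The same sample fails the window rule. Where the participant also returns at Week 8, two samples claim one slot and nothing says which wins. Two programmers following the SAP could build different primary datasets.

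Either choice has a cost. Protocol 2.1 expects the cell-death markers to start moving within 4 weeks, or at the latest within 8, and phenserine is stepped up from 10 to 20 to 30 mg a day. An early sample may therefore carry less effect than a true Week 8 sample. Strict window exclusion instead drops usable samples from a comparator arm of four. Read literally, SAP 2.4 also takes out-of-window laboratory and ECG results out of the secondary analyses, where safety is the key outcome.

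**Working it through.** **The plan's own figure.** Protocol 10.3 gives 4 per arm for 80% power at 2.45 SD, two-sided 0.05. An exact two-sample t-test gives 61.9% at 3 per arm and 82.1% at 4, so the figure reproduces. At the planned 12:4 the power is 97.6%.

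**The conflict.** Adding and subtracting 3 days gives windows of Days 11–17, 25–31, 39–45 and 53–59. Days 18–24, 32–38 and 46–52 belong to no visit.

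- A drop-out sample on Day 17 is at most a Week 2 sample under SAP 2.4. It is the Week 8 value under SAP 3.3, although that window opens 53 − 17 = 36 days later.
- A drop-out sample in one of the gaps enters no primary analysis under SAP 2.4, yet is the Week 8 value under SAP 3.3.
- Under Protocol section 7 the same person may also have a sample near Day 56.

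**If the mapping is applied.** Assume the phenserine effect grows linearly to Week 8, so that a sample on day d carries d/56 of it. Assume also that drop-out occurs in the phenserine arm only, split evenly between Day 14 and Day 28, and is unrelated to outcome. The mean shortfall per mapped person is [(1 − 14/56) + (1 − 28/56)]/2 = (0.75 + 0.50)/2 = 0.625. Attenuation of the Week 8 contrast is drop-out × 0.625:

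| Assumed drop-out | Attenuation |
|---|---|
| 5.9% | 3.7% |
| 10% | 6.3% |
| 23.6% | 14.8% |

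The documents give no planning rate for this trial. In the earlier 12-week trial, at 15 mg twice daily, 23.6% is overall discontinuation and 5.9% is withdrawal for adverse events (Protocol 2.3.1). The 10% is an assumption.

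A 5,000-run simulation at 12:4 with within-person correlation 0.6 agrees. A true 2.45 SD is estimated as 2.30 at 10% drop-out and 2.08 at 23.6%. With samples kept at their actual visit and all visits modelled, both come back to 2.45. If everyone stops at Day 42 the shortfall is 0.25, and attenuation falls to 2.5% and 5.9%.

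Mapping in the small arm weighs more per person. One of 4 donepezil participants mapped from Day 14 shifts the contrast by 0.75/4 = 18.8% of the donepezil Week 8 change. One of 12 on phenserine shifts it by 0.75/12 = 6.3% of the phenserine change.

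**If the window rule is applied.** The 95% half-width in SD units is t × √(1/n₁ + 1/n₂):

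- 12:4: 2.145 × √(1/12 + 1/4) = 2.145 × 0.577 = 1.24
- 12:3: 2.160 × √(1/12 + 1/3) = 2.160 × 0.645 = 1.39, about 13% wider

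So one lost donepezil Week 8 sample removes 1/4 = 25% of the arm from the Week 8 mean difference. In the mixed model it removes 1 of 4 × 4 = 16 donepezil observations, or 6.25%. A lost baseline sample removes the person from both, since no change can be computed.

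If each sample is lost with probability q, the Week 8 mean difference loses at least one of the four donepezil participants with probability 1 − (1 − q)^8 (baseline and Week 8 samples, four people). That is 15%, 34% and 57% at assumed q of 2%, 5% and 10%. Only if complete-case means deleting anyone with any of five samples missing does the exponent become 20, giving 33%, 64% and 88%.

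**The case against.** The strongest reply is that the SAP mostly reads as an available-data plan. One post-baseline sample qualifies for the primary population, early terminators stay in, and the model uses repeated measures. Complete-case is then loose wording. The trial is exploratory and estimation-based, missingness is expected to be limited, and at 12:3 power at 2.45 SD is still 93.9%. Intolerance is first met by dose reduction with treatment continuing (Protocol 6.6), so early stopping may be rare. All of this stands and limits the severity. It does not say which sample is the Week 8 value.

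Several stronger readings are tempting but unsupported:

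- **That both harms occur together.** Mapping and window exclusion cannot act on the same sample. The finding is that the two rules contradict each other.
- **That every lost sample costs a quarter of the comparator arm.** This holds for the Week 8 mean difference, a lost baseline or strict listwise deletion, not for the mixed model.
- **That out-of-window data are discarded or safety data hidden.** They may still be listed and summarised. The safety set has no window condition, and safety is reviewed on an ongoing basis. The defect is the literal wording on secondary analyses.
- **That missingness sensitivity analyses were never planned.** Protocol 10.3 plans them; the SAP does not carry them over.

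The remedy also has a weakness. Someone who stopped early is off drug at Week 8. If the effect vanished entirely off drug, the retrieved samples would dilute the phenserine effect by the full drop-out proportion (10% or 23.6%), more than the mapping does. That is acceptable only as a declared treatment-policy estimand.

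**Conclusion.** The concern holds as a specification conflict that should be fixed. Whatever the drop-out rate, the rules in SAP 2.4, 3.3 and 6 and Protocol section 7 do not yield one Week 8 dataset.

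Applying the mapping can bias the contrast, by about 6% to 15% attenuation for assumed drop-out of 10% to 23.6% with linear onset and stopping at Week 2 or 4. The bias is smaller with later stopping, and it is absent if nobody stops early or the marker does not change over time. The documents fix neither the rate nor the direction. Applying the window rule costs precision: about 13% on the Week 8 interval for one lost donepezil sample, and less in the mixed model.

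Two related points also hold. Association of drop-out with observed covariates cannot exclude dependence on unobserved values, and at most about 0.236 × 16 ≈ 4 drop-outs would be too few to fit such a model. The 12-month endpoint in Protocol 7.2 contradicts the 8-week one in section 7 and matches no visit in the Schedule of Activities; it looks clerical.

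**What to change.** In the SAP, by amendment before database lock:

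1. Delete the mapping sentence in 3.3. Assign each early-termination or out-of-window exosome sample to the nearest scheduled visit by actual day, with a tie-break where two samples fall to one visit. Make the in-window set a sensitivity analysis.
2. Use the Week 8 sample required by Protocol section 7 for Week 8. State that this is a treatment-policy estimand in which off-treatment values may dilute the effect, and add an on-treatment analysis as supportive.
3. Replace the complete-case wording in section 6 with all available post-baseline data in the mixed model, consistent with SAP 4.3 and 7.2.
4. State in 2.4 that safety data are never excluded for timing.
5. Carry the missingness sensitivity analyses of Protocol 10.3 into section 6, and do not present the drop-out regression as evidence for MAR.

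In the protocol, reconcile the 12-month endpoint in 7.2 with the 8-week endpoint in section 7.

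The cost is wording, a small protocol correction and a few extra analyses. The downside is some added timing noise from late or early samples, which the in-window sensitivity analysis will show.

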4.1. Overall Design

Consented patients will undergo a screening visit within 28 days of the planned baseline visit. (For women of childbearing potential, a negative serum pregnancy test will be required within 1 day prior to receiving the first dose of study drug). Only those patients who complete screening and meet study eligibility criteria at baseline will be randomized 6:2 to receive phenserine or donepezil in an open-label manner. The first dose of study medication will be taken in the clinic, and the participant will be instructed on how to continue dosing at home until their next visit.

Participants will visit the clinic for safety and other planned study assessments at 2-week intervals through the 8-week treatment period, as detailed in the Schedule of Activities ([Table 1](#)).

Patients who withdraw or discontinue from the study before Week 8 will have an early termination visit within one week of discontinuation that includes safety follow-up. For participants who complete the study, a final follow-up safety assessment will be conducted within one week after completion of dosing.

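### SAP 3.3 moves early-termination visits to Week 8, SAP 2.4 keeps out-of-window assessments out of the primary analysis, and no rule says which prevails or which record counts

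*SAP*

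**What the plan says.** SAP 3.3 (Withdrawal and Follow-up): "Early termination visits will be mapped to the end-of-treatment time point where applicable". The qualifier at the end of that sentence is not defined. The SAP 2.4 table identifies the time point as "V5: Week 8 / End of Treatment", Day 56 ± 3.

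SAP 2.4 also gives the window rule twice: "Only assessments obtained within the protocol-specified windows will be used for primary and secondary analyses", and "Assessments collected outside the visit window will not be included in the primary analysis but may be listed and summarized descriptively". Neither sentence makes an exception for early termination.

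SAP 6 adds "No imputation will be performed for missing biomarker or cognitive data" and "Analyses will use observed data only in a complete-case manner". It includes early terminators where they have data, but does not say at which visit.

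Protocol 4.1 says that people who stop before Week 8 "will have an early termination visit within one week of discontinuation that includes safety follow-up". Protocol 7 says that after withdrawal from treatment "all endpoint assessments will be carried out at the point of drop-out and at the 8-week endpoint unless consent is withdrawn". Protocol 7.2 repeats that provision with a 12-month endpoint in place of the 8-week one.

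The model in SAP 7.2 has treatment, visit as a category (Weeks 2, 4, 6, 8) and their interaction, with an unstructured covariance preferred.

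**The concern.** With a categorical visit and an interaction, a sample's visit label decides which treatment contrast it informs. Week 8 closes the primary timeframe in the SAP 4.5 outcome table. Under SAP 3.3, a sample taken weeks earlier, possibly at a lower scheduled dose or shortly after stopping, would be analysed as a Week 8 response. Under SAP 2.4 the same sample would not enter the Week 8 contrast. A programmer cannot follow both.

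There is also a record-selection gap. A participant who stops treatment and is followed under Protocol 7 has a drop-out record and a true Week 8 record. If the first is relabelled, that person has two rows at one visit, which an unstructured within-person covariance does not accommodate. Nothing says which row is kept.

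FLAME, MoCA and the blood and CSF markers have a single post-baseline point in Table 1 (Week 8), so a mapped value would supply the whole change score. These outcomes are exploratory. The SAP 2.4 exclusion names only primary and secondary analyses, so the direct conflict concerns those; for the exploratory outcomes the mapping rule would operate unopposed by a window rule.

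**Working it through.** **1. Can both rules be obeyed?** The Week 8 window is Day 56 ± 3, that is Days 53–59.
- Early-termination visit on Days 53–59: already Week 8 under SAP 2.4, so no mapping is needed.
- Early-termination visit before Day 53: SAP 3.3 puts it at Week 8; SAP 2.4 bars it from Week 8 in the primary analysis.

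The mapping sentence therefore has an effect only where it breaks the window rule.

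**2. How early, and at what scheduled dose?** (SAP 2.4; Protocol 6.6)

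| Day of sample | Days before target (56 − day) | Days before window opens (53 − day) |
|---|---|---|
| 14 | 42 | 39 |
| 28 | 28 | 25 |
| 42 | 14 | 11 |

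Scheduled phenserine is 2 × 5 = 10 mg/day in Weeks 1–2, 2 × 10 = 20 mg/day in Weeks 3–4, and 3 × 10 = 30 mg/day in Weeks 5–8.

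**3. Could the sample be off drug?** Protocol 4.1 allows up to 7 days between discontinuation and the visit. Protocol 4.5 gives a half-life of 8.25 h for AChE inhibition. After 24 h the remaining fraction is 0.5^(24/8.25) = 0.13; 7 days is 168/8.25 = 20.4 half-lives. This bears on AChE inhibition. The documents give no decay rate for the exosome markers.

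**4. Illustrative size.** Arm sizes are 12 and 4 (SAP 3). Assume a simple Week 8 arm mean, k of 12 phenserine participants mapped, and a fraction f of the maintenance-dose effect present in their samples. Dilution = (k/12) × (1 − f).

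| k | f = 0 | f = 0.5 |
|---|---|---|
| 1 | 8.3% | 4.2% |
| 2 | 16.7% | 8.3% |
| 3 | 25.0% | 12.5% |

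Both k and f are assumptions. In the donepezil arm one participant carries 1/4 = 25% of the mean, so a mapped value 1 SD off moves that mean by 0.25 SD, against 1/12 = 0.08 SD for one phenserine participant.

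**5. What does enforcing the window cost?** The plan's own figure reproduces: at 2.45 SD and two-sided 0.05, the noncentral t gives 61.9% power with 3 per arm and 82.1% with 4, so 4 per arm is the smallest size reaching 80%. The point does not depend on it. For one measurement per person and unit SD, the 95% CI half-width is t(0.975; n1+n2−2) × √(1/n1 + 1/n2).

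| Phenserine : donepezil | Half-width (SD) | Power at 2.45 SD |
|---|---|---|
| 12 : 4 | 1.24 | 97.6% |
| 11 : 4 | 1.26 | 97.2% |
| 9 : 4 | 1.32 | 95.9% |
| 12 : 3 | 1.40 | 93.9% |

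**6. How many early samples keep a place?** The Week 2, 4 and 6 windows are Days 11–17, 25–31 and 39–45: 3 × 7 = 21 of the 42 days from Day 11 to Day 52. An exosome sample on the other 21 days, or before Day 11, would be listed only.

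**The case against.** The best counter-argument is that the mapped group may be nearly empty. Protocol 7 separates participants who withdraw consent, for whom no further assessments can be made, from those withdrawn from treatment, who stay in and are assessed at Week 8. Mapping fills an empty Week 8 cell only for someone with a drop-out sample and no later one. This stands: the table in step 4 is an illustration, and it would be wrong to apply it to every discontinuer. The duplicate-record gap, however, arises precisely when Protocol 7 is followed.

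The undefined qualifier might be read as limiting the mapping to in-window visits. On that reading the sentence does nothing, and it should say so.

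Protocol 4.1 describes the early-termination visit in terms of safety follow-up, Table 1 has no column for it, and Protocol 7 places endpoint assessments at the point of drop-out. So an off-drug exosome sample is possible, not established.

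The study is exploratory and estimation-based, which lowers the stakes. But the Week 8 estimate is a main product of such a study, so its dataset should be unambiguous.

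A reader might infer that the rule is imputation under another name and that three SAP rules yield three Week 8 datasets. Relabelling an observed value is not strictly imputation. It sits poorly with SAP 6 because it fills an empty cell with an earlier value, but only SAP 3.3 against SAP 2.4 is a direct conflict, which gives two datasets.

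**Conclusion.** SAP 3.3 and SAP 2.4 conflict as written for any early-termination visit before Day 53, and no rule chooses between a drop-out record and a true Week 8 record. That follows from the text alone. The size is not determinable from the documents; about 4–25% dilution of the Week 8 phenserine effect holds only if 1 to 3 of 12 participants are mapped and their samples carry 0–50% of the effect. Enforcing the window costs little precision under the plan's own assumptions.

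Two stronger readings are not supported:
- That mapping would load Week 8 with the people who tolerated phenserine least. The 23.6% discontinuation in Protocol 2.3.1 is all-cause; adverse-event withdrawals there were 5.9%, against 6.1% on placebo. Protocol 6.6 answers intolerance with dose reduction and continuation, so Week 8 includes lower doses by design.
- That the dataset would be picked after results are seen. SAP 1.1 has the plan finalised, and any deviation documented by amendment, before database lock; finalisation also precedes unblinding of biomarker results. The ambiguity can be closed in that interval.

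**What to change.** By SAP amendment before database lock, replace the mapping sentence with:

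> Early-termination assessments are assigned, by actual study day, to the scheduled visit whose window contains that day, including Week 8 if on Days 53–59. Otherwise they are listed only and are not relabelled as Week 8. If an early-termination and a scheduled record fall in the same window, the record closest to the target day is used. Week 8 samples taken after stopping treatment are analysed at Week 8 and flagged as off treatment.

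Also:
- Add a sensitivity analysis restricted to on-treatment samples. The main analysis keeps off-treatment Week 8 samples, so the new wording corrects the labelling; it does not remove dilution from people who stopped.
- State in SAP 6 that complete-case does not drop the in-window Week 2–6 records of early terminators.
- Reconcile the 8-week text in Protocol 7 with the 12-month text in Protocol 7.2.

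The cost is wording, plus a few out-of-window values listed instead of analysed. The loss is felt most for FLAME and MoCA, which have no other post-baseline visit to fall back on.
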